#### **6.6.7 Emergency unblinding of treatment assignment**

Not applicable, since this is an open-label study.

#### **6.6.8 Study completion and post-study treatment**

For all patients who were included into this study (i.e., who signed informed consent and are randomized), whether discontinued the study treatment prematurely or completed the study, the final examination 12 months after randomization (Visit 9) will be performed.

The investigator also must provide follow-up medical care for all patients who are prematurely withdrawn from the study, or must refer them for appropriate routine care according to center practice.

## **7 Visit schedule and assessments**

[Table 2](#) lists all of the assessments and indicates with an "X" the visits when they are performed.

Patients should be seen for all visits on the designated day or as close to it as possible. During first month of treatment (until Visit 5) a time interval of  $\pm$  3 days and  $\pm$ 14 days thereafter may be acceptable. For the final visit (Visit 9) a time interval of 30 days is acceptable.

Patients who discontinue study drug before completing the study, and those who prematurely withdraw from the study for any reason, should be scheduled for a visit as soon as possible, at which all of the assessments listed for the EoT visit (visit 9a) will be performed.

At a minimum, they will be contacted for safety evaluations during the 30 days following the last dose of study drug, including final contact at the 30-day point. Documentation of attempts to contact the patient should be recorded in the patient record.

All data obtained from the assessments listed in [Table 2](#) and described in detail in the subsections below must be supported by the patient's source documentation.

**Table -2 Assessment schedule**

Phase	Screening 	Baseline 	Treatment Phase						EOT 	EOS
Visit	1	2	3	4	5	6	7	8	9a	9
Days		1	8	15	30	90	180	270		360
Month					1	3	6	9		12
Informed consent	X									
Inclusion/ exclusion	X	X								
Randomization		X								
Demography	X									
General medical history	X									
Transplantation information	X									
Physical examination	X	X	X	X	X	X	X	X	X	X
Vital signs	X	X	X	X	X	X	X	X	X	X
Laboratory test:										
- Hemat. / Biochemistry		X	X	X	X	X	X	X	X	X
GFR		X	X	X	X	X	X	X	X	X
Urinalysis		X		X	X	X	X	X	X	X
Viral Serology	X									
CMV Monitoring	X	X		X	X	X	X	X	X	X
HCV Monitoring										
Viral load (RNA-level)	X	X 		X 	X 					
Genotype	X									
Pregnancy test  (β-HCG)	X	X								X
Liver Doppler		X								
Ultrasound 										
Tacrolimus C0 level		X	X	X	X	X	X	X	X	X
Everolimus C0 level			X	X	X	X	X	X	X	X
Rejection episodes		X 	←———— as necessary —————→							
Biopsies 			←———— as necessary —————→						X	
Infections			←———— as necessary —————→						X	
AEs			←———— as necessary —————→						X	
SAEs			←———— as necessary —————→						X	
Comments			←———— as necessary —————→							
Concomitant therapy			←———— as necessary —————→							
Immunosuppressive therapy			←———— as necessary —————→							
End of treatment / End of study								X	X	

- 1) day 21-day of transplantation
- 2) Visit 2 (Baseline) has to be performed prior to randomization, 7-21 days after Tx.
- 3) End of Treatment Visit in case of premature study discontinuation
- 4) Only in HCV positive Patients
- 5) Only in women of childbearing potential

- 6) Liver Doppler Ultrasound of the hepatic artery, hepatic vein, portal vein, and inferior vena cava will be carried out up to 5 days prior to randomization.
  - 7) Intraoperatively
  - 8) For analysis of allograft fibrosis (only HCV positive patients)
- 

### **Screening Visit - Visit 1 (day -21 to Tx)**

1. Patient signs informed consent.
2. Patient's eligibility for the study according to in- and exclusion criteria will be checked.
3. Demographic data will be recorded (sex, age, ethnic origin).
4. Relevant medical history will be obtained and recorded until time point of randomization.
5. Transplantation information will be recorded (donor and recipient information).
6. A complete physical examination will be performed.
7. Vital signs will be measured.
8. Venous blood will be drawn for measurement of viral serology (HBsAg, HCV).
9. Venous blood will be drawn for CMV monitoring (including pp65 Ag).
10. Venous blood will be drawn for HCV monitoring: Viral load (RNA level), HCV genotype (only at screening)
11. Menopausal status will be recorded and in all women of childbearing potential a pregnancy test will be performed ( $\beta$ -HCG) (see also section 7.3).
12. An intraoperative biopsy (preferably after reperfusion) will be performed for analysis of allograft fibrosis (only HCV positive patients).

### **Baseline Visit - Visit 2 (day 1)**

The Baseline assessment has to be performed prior to randomization.

1. Patient's eligibility for the study according to in- and exclusion criteria will be checked.
2. A complete physical examination will be performed.
3. Vital signs will be measured.
4. Urinalysis will be performed.
5. Venous blood will be drawn for measurement of hematology and biochemistry.
6. Glomerular Filtration Rate (GFR) will be calculated.
7. Venous blood will be drawn for HCV monitoring: Viral load (RNA level), in HCV positive patients only.
8. Venous blood will be drawn for measurement of the tacrolimus C0-h blood levels.
9. Prior/Concomitant medications / significant non-drug therapies will be recorded.
10. Patients eligible for the study will be randomized to one of the two treatment groups.
11. Study drug intake will be performed within 24h.
12. Information on rejection episodes biopsies, hospitalization, infections, and other (S)AEs that occurred since the last visit will be recorded.

### **Treatment phase – Visits 3, 4, 5, 6, 7, and 8 (Day 8, 15, Month 1, 3, 6, 9)**

1. A complete physical examination will be performed at each study visit.
2. Vital signs will be measured at each study visit.
3. Returned study medication (everolimus) and returned tacrolimus will be counted. Patient will be provided with new study medication (if necessary) and dosing instructions for drug intake until following visit.
4. Venous blood will be drawn for measurement of hematology and biochemistry at each study visit.
5. Venous blood will be drawn at Month 1, 3, 6, and 9 for CMV monitoring (including pp65 Ag).
6. Venous blood will be drawn at Month 1, 3, 6, and 9 for HCV monitoring in HCV positive patients only: Viral load (RNA level).
7. Venous blood will be drawn for measurement of the tacrolimus and everolimus C0-h blood levels.
8. Urinalysis will be performed at Month 1, 3, 6 and 9.
9. Glomerular Filtration Rate (GFR) will be calculated at each study visit.
10. Changes in Concomitant medications / significant non-drug therapies will be recorded at each study visit.
11. (Changes in) Immunosuppressive medication will be recorded at each study visit.
12. Information on rejection episodes, biopsies, hospitalization, infections, and other (S)AEs that occurred since the last visit will be recorded.

### **End of Treatment/End of Study – Visit 9a and Visit 9 (Month 12)**

In case of early discontinuation of study drug treatment, Month 12 assessments need to be performed

- as soon as possible after study drug discontinuation (Visit 9a).
- additionally at the originally planned time point, i.e. 12 months post randomization (Visit 9). At Month 12 for patients who discontinued study drug prematurely, only the following numbers 1, 2, 4, 5, 6, 8, 9, and 13 are mandatory.

1. A complete physical examination will be performed.
2. Vital signs will be measured.
3. Returned study medication (everolimus) and returned tacrolimus will be counted.
4. Venous blood will be drawn for measurement of hematology and biochemistry.
5. Venous blood will be drawn for CMV monitoring (including pp65 Ag).
6. Venous blood will be drawn for HCV monitoring: Viral load (RNA level), in HCV positive patients only.
7. Venous blood will be drawn for measurement of the tacrolimus and everolimus C0-h blood levels.
8. Urinalysis will be performed.
9. GFR will be calculated.
10. A control biopsy will be performed for analysis of allograft fibrosis (only HCV positive patients).

11. End of Study / End of Treatment information will be obtained.
12. Menopausal status will be recorded and in all women of childbearing potential a pregnancy test will be performed ( $\beta$ -HCG) (see also section 7.3).

For patients who prematurely discontinued study drug, information about rejection episodes, biopsies, opportunistic infections, malignancies and the current immunosuppression will be collected. SAEs will be collected until 30 days after the patient has stopped study participation (or longer in case of suspected relationship).

## **7.1 Information to be collected on screening failures**

Only demography data and the reason for failing (screening failure log) are collected for those patients who fail to enter the treatment phase.

## **7.2 Patient demographics/other baseline characteristics**

The following demographic data and other baseline characteristics will be recorded:

- **Demography:** age, sex, and ethnic origin
- **Relevant medical history / current medical conditions:**

Relevant prior diseases and surgeries as well as concomitant diseases will be recorded with date of diagnosis / surgery and information on whether it is an active problem.

For women, the menopausal status will be recorded. The pregnancy test (e.g.  $\beta$ -HCG) will be performed locally within 7 days prior to visit 1, 2 and 9. Results must be available and negative prior to administration of study medication and reported on the CRF.

## **7.3 Transplantation information**

### Donor information:

Viral serology on CMV, EBV, HCV, HBsAg.

### Recipient information:

Viral serology on CMV, EBV, HCV, HBsAg, underlying liver disease prior to transplantation

## **7.4 Immunosuppressive Drugs/Compliance**

Records of all immunosuppressive drugs (induction therapy, CS, MMF, everolimus, tacrolimus) used and dosages administered are to be kept during the study. All changes to the medication dosing regimen should be recorded in the Dosage Administration Record CRF, along with the reason for change and dates.

Compliance will be assessed by the investigator and/or study personnel at each visit using pill counts and information provided by the patient. This information should be captured in the source document at each visit.

## 7.5 Efficacy

The following efficacy variables will be obtained and recorded:

### Renal function

Renal function will be assessed by measuring serum creatinine, serum cystatin C by Hoek's formula, and estimated GFR (eGFR) by CKD EPI, by Cystatin C-based Hoek's formula, MDRD-4, Nankivell and Cockcroft-Gault and proteinuria as determined by a spot urine protein/creatinine ratio. The evolution of renal function by chronic kidney disease strata (CKD) will be evaluated. The incidence of and time to renal replacement therapy will be assessed and the incidence of proteinuria at various timepoints will be evaluated.

- **Serum creatinine and serum cystatin C**

For the analysis of serum creatinine and serum cystatin C, venous blood will be drawn and analyzed in the center's local laboratory.

- **Glomerular Filtration Rate (GFR)**

The GFR is the best clinical estimate of renal function in health and disease, and correlates well with the clinical severity of renal function disturbances. Several studies have shown that in patients with progressive renal disease, GFR declines or reciprocal serum creatinine and cystatin C levels respectively elevate linearly over time in a predictable manner.

With the help of the serum creatinine and cystatin C values respectively, the GFR [ml/min] will be calculated via the following formulas:

#### **Nankivell formula**

cGFR will be estimated as  $6.7/(SCr \times 0.0884) + 0.25 \times \text{weight} - 0.5 \times \text{urea} - 100/\text{height}^2 + 35$  (25 for women).

#### **Hoek's formula**

cGFR will be estimated as  $-4.32 + 80.35/\text{cystatin C [mg/L]}$ .

#### **CKD EPI**

The CKD-EPI equation, expressed as a single equation, is  $\text{GFR} = 141 \times \min(\text{Scr}/\kappa, 1)^\alpha \times \max(\text{Scr}/\kappa, 1)^{1.209} \times 0.993^{\text{Age}} \times 1.018$  [if female]  $\times 1.159$  [if black], where Scr is serum creatinine,  $\kappa$  is 0.7 for females and 0.9 for males,  $\alpha$  is -0.329 for females and -0.411 for males, min indicates the minimum of Scr/ $\kappa$  or 1, and max indicates the maximum of Scr/ $\kappa$  or 1 (Levey et al., 2009).

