#### **MDRD-4 formula**

$\text{eGFR [mL/min/1.73m}^2\text{]} = \text{eGFR} = 186.3 \times \text{C}^{-1.154} \times \text{A}^{-0.203} \times \text{G} \times \text{R}$ , where  
C is the serum concentration of creatinine [mg/dL],  
A is age (years), G=0.742 when gender is female, otherwise G=1,  
R=1.21 when race is black, otherwise R=1.

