### **10.4.1 Variable**

The primary efficacy variable of this trial is the renal function at Month 12 after baseline assessed by estimated GFR based on recalculated values according to the MDRD-4 formula:  $eGFR [mL/min/1.73m^2] = eGFR = 186.3 * C^{1.154} * A^{-0.203} * G * R$ , where C is the serum concentration of creatinine [mg/dL], A is age (years), G=0.742 when gender is female, otherwise G=1, R=1.21 when race is black, otherwise R=1.

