## **10.7 Sample size calculation**

The trial tests the null hypothesis that there is no difference in renal function, estimated by cGFR according to the MDRD-4 formula, at 12 months after randomization between the everolimus-based tacrolimus-minimization regimen and the tacrolimus-based control regimen versus the alternative hypothesis that the difference is 7.0 ml/min/1.73m^2. A sample size of 105 in each group will have 80% power to detect a difference in means of 7.0 ml/min/1.73m^2 assuming that the common standard deviation is 18.0 ml/min/1.73m^2 with a 5% two-sided significance level. (One will decide in favor of H1 when the difference in means would be 5.1 ml/min/1.73m^2 or greater in favor of the everolimus-based group.) To adjust the sample size for a common drop-out rate (DOR) of 20% (using the formula  $N_{adj}=N/(1-DOR)^2$ ), 165 patients need to be randomized per group. Sample sizes were estimated using NQuery (Version 6.1) procedure “Two-group *t*-test for equal means (equal n’s)”.

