### **2.3.3 Primary endpoint**

The primary objective of the trial was to demonstrate that an immunosuppressive regimen based on everolimus (EVR) in co-exposure with tacrolimus (TAC) has superior efficacy compared to tacrolimus alone on estimated glomerular filtration rate (MDRD-4 formula) at 12 months after transplantation in de novo liver transplant recipients.

The primary efficacy variable of this trial is the renal function at Month 12 after baseline assessed by estimated GFR based on recalculated values according to the MDRD-4 formula:

$$\text{eGFR [mL/min/1.73m}^2\text{]} = \text{eGFR} = 186.3 * C^{-1.154} * A^{-0.203} * G * R,$$

where C is the serum concentration of creatinine [mg/dL], A is age (years), G=0.742 when gender is female, otherwise G=1, R=1.21 when race is black, otherwise R=1.

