### **Renal function-related objectives**

Renal function as assessed by eGFR calculated according to the CKD-EPI, Cockcroft-Gault, Nankivell, and Hoek formulas were the further renal function-related secondary parameter. Further parameter was the proteinuria.

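### Protocol 7.5 prints the CKD-EPI formula with a positive exponent above kappa, and protocol 10.4.1 prints MDRD-4 with a creatinine sign that contradicts protocol 7.5 and the SAP

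*Protocol*

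**What the plan says.** **CKD-EPI.** Protocol 7.5 builds the estimate from a term that acts when creatinine is below kappa and a term that acts when it is above. Kappa "is 0.7 for females and 0.9 for males". The exponent of the lower term "is -0.329 for females and -0.411 for males". The upper term is printed, in typesetting notation, as "\max(\text{Scr}/\kappa, 1)^{1.209", with no minus sign. The section cites a published source for the equation.

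The SAP lists the equation among its secondary renal measures (section 2.5.1: "Renal function as assessed by eGFR calculated according to the CKD-EPI, Cockcroft-Gault, Nankivell, and Hoek formulas") and applies the primary ANCOVA model to it in section 2.5.2. It does not print the equation, and its reference section is empty.

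**MDRD-4, the primary variable.** This formula appears three times:
- Protocol 7.5: "186.3 \times \text{C}^{-1.154} \times \text{A}^{-0.203"
- Protocol 10.4.1: "186.3 * C^{1.154} * A^{-0.203} * G * R"
- SAP 2.3.3: "186.3 * C^{-1.154} * A^{-0.203} * G * R"

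The first and third give creatinine a negative exponent. Protocol 10.4.1, the protocol section that defines the primary variable, gives it a positive one.

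**The concern.** An estimate of GFR should fall as creatinine rises, and the documents themselves treat it that way. In protocol 7.5, Nankivell and Cockcroft-Gault put creatinine in a denominator, and MDRD-4 gives it a negative power. Protocol 6.6.3 treats a rise in serum creatinine as acute kidney injury. CKD-EPI as printed follows this direction up to kappa and then turns round. MDRD-4 as printed in 10.4.1 runs the wrong way throughout.

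For CKD-EPI, the protocol's formula is the only one the documents print. A programmer working from it literally would give the patients with the worst renal function the highest values. A named secondary renal analysis, reported with confidence intervals and exploratory p values, could then point the wrong way. For MDRD-4, the risk is that two protocol sections and the SAP disagree on how the primary variable is calculated.

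**Working it through.** **1. The plan's own figure.** Protocol 10.7 states: "A sample size of 105 in each group will have 80% power". The inputs are a difference of 7.0, SD 18.0 and 5% two-sided significance. A two-sample t-test needs 104.77, so 105 per group, with power 80.1%. The drop-out adjustment is 105/(1 − 0.20)² = 164.06, so 165. Both figures reproduce. Neither depends on the eGFR formula, so the sample size is not affected.

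**2. Inputs for the formula check.** Constants and exponents are those printed in protocol 7.5 and 10.4.1. The patient is an assumption: non-black man, age 55. The minus sign on 1.209 is inferred from the direction of the other formulas, because the documents print −1.209 nowhere.

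**3. CKD-EPI at creatinine 1.5 mg/dL.** The age-adjusted constant is 141 × 0.993^55 = 95.81. The upper term is 1.5/0.9 = 1.667.
- As printed: 95.81 × 1.667^1.209 = 95.81 × 1.8545 = 177.7
- With the minus sign: 95.81 × 1.667^(−1.209) = 95.81 × 0.5392 = 51.7

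**4. MDRD-4 at creatinine 1.5 mg/dL.** The age-adjusted constant is 186.3 × 55^(−0.203) = 82.59.
- As printed in 10.4.1: 82.59 × 1.5^1.154 = 131.9
- As in protocol 7.5 and the SAP: 82.59 × 1.5^(−1.154) = 51.7

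**5. Over the creatinine range (mL/min/1.73m²).**

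| Creatinine, mg/dL | CKD-EPI as printed | CKD-EPI with minus | MDRD-4 per 10.4.1 | MDRD-4 per 7.5 and SAP |
|---|---|---|---|---|
| 0.5 | 122.0 | 122.0 | 37.1 | 183.8 |
| 0.9 | 95.8 | 95.8 | 73.1 | 93.3 |
| 1.2 | 135.7 | 67.7 | 101.9 | 66.9 |
| 2.0 | 251.6 | 36.5 | 183.8 | 37.1 |
| 3.0 | 410.8 | 22.3 | 293.4 | 23.2 |

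CKD-EPI as printed is V-shaped, with its minimum at kappa. The 10.4.1 version of MDRD-4 rises throughout.

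**6. Two simple contrasts.**
- Everolimus 1.0 against control 1.2 mg/dL: CKD-EPI gives −26.8 as printed and +16.7 with the minus sign.
- Everolimus 0.6 against control 0.8 mg/dL, both below kappa: +12.6 either way.

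**7. Group means under the planned effect.** MDRD-4 eGFR was taken as normal with SD 18 and a benefit of 7.0 (protocol 10.7). The control mean is assumed to be 60, 70 or 80, values are limited to 15 to 140, and every patient is the assumed man of 55. Creatinine was back-calculated from the correctly signed MDRD-4 and the other formulas were then applied. Entries are everolimus minus control.

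| Assumed control mean | CKD-EPI with minus | CKD-EPI as printed | MDRD-4 per 10.4.1 |
|---|---|---|---|
| 60 | +7.1 | −22.5 | −16.2 |
| 70 | +6.7 | −14.5 | −11.2 |
| 80 | +5.9 | −8.9 | −8.2 |

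Between 64% and 97% of patients in a group have creatinine above 0.9 mg/dL in these scenarios. That is why the mean difference reverses even though the lower branch of CKD-EPI is sound.

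**The case against.** **It may be an extraction fault.** Each discrepancy is one superscript minus sign in machine-read text. The SAP repeats the 10.4.1 definition almost verbatim and has the minus. Against this, other minus signs survived in the same two formulas: the age exponent in 10.4.1 and both lower exponents in CKD-EPI. The artefact is possible but not shown, so the original PDF has to be checked first.

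**The primary result is protected.** A reader might infer that the primary treatment effect would change sign. The documents do not support that. The SAP sets out how the analysis is implemented, and its formula is correctly signed, as is protocol 7.5. The reversal would occur only if 10.4.1 were followed against both. This stands.

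**CKD-EPI is exploratory.** A reader might take it for a sensitivity check on the primary result. It is not one. The supportive analyses in protocol 10.4.4 and SAP 2.3.6 are the per-protocol ANCOVA and the mixed model, with multiple imputation treated as a further alternative. This stands.

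**The reversal is not universal.** It would be wrong to say that printed CKD-EPI always rises with creatinine, because below kappa it behaves properly.

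**The error would probably be noticed, and the source is cited.** In step 7 the printed formula gives group means of about 114 to 173, against 60 to 86 with the minus sign. Such values would look odd beside MDRD-4, and a programmer could consult the cited paper. Both points lower the risk, but a plan should not rely on either.

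**Section 7.5 does not settle the direction in words.** Its remark on GFR and reciprocal creatinine is garbled and cannot be cited as saying that GFR falls as creatinine rises. The direction rests on the other formulas and on section 6.6.3.

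**Conclusion.** The point holds in two parts of unequal weight.

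The CKD-EPI formula as supplied has the wrong direction above kappa, and nothing else in the documents corrects it. For the assumed patient at 1.5 mg/dL the value is 177.7 instead of 51.7. In the assumed scenarios a difference of about +6 to +7 becomes about −9 to −22. The sizes depend on the assumed age, sex, race and control means, which the documents do not give. The direction depends only on the printed exponent and on enough patients having creatinine above kappa. What is affected is an exploratory secondary analysis.

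The MDRD-4 formula in protocol 10.4.1 contradicts protocol 7.5 and SAP 2.3.3. This is an inconsistency in the definition of the primary variable and should be reconciled. It does not show that the primary analysis was or would be wrong.

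Both parts are conditional on the minus signs being absent from the original PDF.

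**What to change.** 1. Check both formulas in the original PDF. If the minus signs are there, nothing in the documents needs changing.
2. If they are missing, change the CKD-EPI upper exponent in protocol 7.5 to −1.209, confirming it against the source that the section cites. Change the creatinine exponent in protocol 10.4.1 to −1.154, to agree with protocol 7.5 and the SAP.
3. Before database lock, confirm that every programmed creatinine-based eGFR falls as creatinine rises, for both sexes and on both sides of kappa.

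Reprinting the remaining eGFR formulas in the SAP would be a convenience. No sign error is alleged in Cockcroft-Gault, Nankivell or Hoek, so it is not required.

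The cost is two minus signs and one short program check. Data collection, patients and sample size are unaffected.
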